## **9 Removal of Subject from Study**

### **9.1 Discontinuation of Study**

The Principal Investigator reserves the right to discontinue this study at any time. Should this occur, the appropriate authorities (eg, Institutional Review Board, FDA, and the funding agency) will be informed, and the reason for discontinuation will be indicated in the Case Report Form (CRF). A study termination CRF must be completed.

### **9.2 Withdrawal from Study**

#### **9.2.1 Discontinuation of Study Drug**

The Principal Investigator will discontinue dosing a subject if he believes it is in the subject's best interest. When a subject discontinues receiving study drug, the subject should be followed for 30 days from the last dose. The date that the subject discontinues receiving study drug will be recorded. Subjects experiencing adverse reactions that are believed to be related to the study drug should be followed until the reaction has resolved, stabilized, or are otherwise explained.

#### **9.2.2 Early Withdrawal/Study Termination**

Reasons why a subject may discontinue or be withdrawn from the study include, but are not limited to; intolerance to study drug, an adverse event, subject request, or investigator request.

## **10 Adverse event reporting**

### **10.1 Definition and Grading Intensity of Adverse Events (AE)**

An adverse event is the appearance or worsening of any undesirable sign, symptom, or medical condition occurring after starting the study drug even if the event is not considered to be related to study drug. Study drug includes the investigational drug under evaluation and the comparator drug or placebo that is given during the study. Medical conditions/diseases present before starting study drug are only considered adverse events if they worsen after starting study drug. Abnormal laboratory values or test results constitute adverse events only if they induce clinical signs or symptoms, are considered clinically significant, or require therapy.

The occurrence of adverse events should be sought by non-directive questioning of the patient at each visit during the study. Adverse events also may be detected when they are volunteered by the patient during or between visits, through physical examination, laboratory tests, or other assessments. Adverse events will be collected for up to 4 weeks after completion of study drug administration. All adverse events must be recorded on the Adverse Events eCRF with the following information:

1. the severity grade (mild, moderate, severe)
2. its relationship to the study drug(s)
3. its duration (start and end dates or if continuing at final exam)
4. whether it constitutes a serious adverse event (SAE)

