### **4 Experimental Plan**

#### **4.1 Study Design**

This is a single-center, randomized, prospective, double-blind, placebo-controlled study. Eligible subjects who enroll in this study will be randomized prior to discharge from the initial transplant hospitalization in a 1:2 ratio standard of care (placebo), or 90 days of once-daily ciprofloxacin. Patients will be stratified based on the use of alemtuzumab (Campath) induction.

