### **6.4 Procedures**

#### **6.4.1 Pre-treatment Data Collection**

BK PCR from plasma will be collected during the initial hospital visit prior to study drug administration (per standard of care). Study drug will be initiated upon discharge from initial hospitalization, and no later than day 7 post-transplant.

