#### **6.4.2 Post-treatment Data Collection**

Patients will remain on study medication for 90 days post-transplant. All routine standard of care procedures/visits will apply. Patients are to have routine BK PCR drawn at 1, 2, 3, 6, 9, and 12 months post-transplant. Study visits will occur at baseline, 2 weeks, and 1, 2, 3, 6, 9, and 12 months post-transplant.

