### 6.5.1 Sequence of Events

Time of Visit	Screening/Baseline -14 to 7 days post transplant	2 Weeks Post TXP	1 Month Post TXP	2 Months Post TXP	3 Months Post TXP	6 Months Post TXP	9 Months Post TXP	12 Months Post TXP
Visit Window	N/A	±7 Days	± 7 Days	± 7 Days	± 14 Days	±14 Days		
Visit Number	1	2	3	4	5	6	7	8
Inclusion/Exclusion criteria	X (R)							
Informed consent	X (R)							
Med History 	X (R)							
Concomitant Medications 	X (R)	X (R)	X (R)	X (R)	X (R)	X (R)	X (R)	X (R)
Transplant Data Collection 	X (R)							
Randomization 	X (R)							
Study Medication Dispensation or Return	X (R)	X (R)	X (R)		X (R)			
Study medication record	X (R)	X (R)	X (R)		X (R)			
BK PCR (serum)	X (SOC)		X (SOC)	X (SOC)	X (SOC)	X (SOC)	X (SOC)	X (SOC)
AE/SAE Assessment	X (R)	X (R)	X (R)	X (R)	X (R)			
Serum Creatinine	X (SOC)		X (SOC)		X (SOC)	X (SOC)	X (SOC)	X (SOC)
Urine Analysis and culture (if applicable) and blood cultures	X (SOC)	X (SOC)	X (SOC)	X (SOC)	X (SOC)	X (SOC)		
Tacrolimus/Sirolimus levels	X (SOC)	X (SOC)	X (SOC)	X (SOC)	X (SOC)	X (SOC)	X (SOC)	X (SOC)
Urine Protein to Creatinine Ratio			X (SOC)	X (SOC)	X (SOC)	X (SOC)	X (SOC)	X (SOC)

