### **10.3 Serious Adverse Event**

A Serious Adverse Event (SAE) is any adverse event occurring for up to 4 weeks after completion of study drug administration that results in any of the following outcomes:

- Death
- Graft loss
- A life threatening event which may place the patient at an immediate risk of death
- Persistent or significant disability
- Hospitalization for administration of intravenous antibiotics due to presence of multidrug resistant infection
- Cardiac arrhythmia
- Tendon rupture

SAEs considered "definitely" related to the study drug must be submitted to IRB.

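### The schedule's last AE/SAE assessment is at month 3, at least 12 days before the post-dose safety window closes for any full-course subject, and this contradicts section 10.1

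*Combined protocol and SAP*

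**What the plan says.** **Safety window.** Section 10.1 of the combined protocol and SAP states: "Adverse events will be collected for up to 4 weeks after completion of study drug administration". Section 10.3 defines an SAE as "any adverse event occurring for up to 4 weeks after completion of study drug administration" that leads to one of the listed outcomes.

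**Treatment period.** Section 6.4.2 says: "Patients will remain on study medication for 90 days post-transplant". Section 4.1 describes the active arm as "90 days of once-daily ciprofloxacin", and section 6.4.1 sets the start: "Study drug will be initiated upon discharge from initial hospitalization, and no later than day 7 post-transplant".

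**Assessments.** In the table in 6.5.1, the row "AE/SAE Assessment" is marked in the first five columns (screening/baseline, 2 weeks, and months 1, 2 and 3). It is blank at months 6, 9 and 12. Section 6.4.2 lists no visit between months 3 and 6.

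**Text that points the other way.** Section 10.1 also says that AEs are to be "sought by non-directive questioning of the patient at each visit during the study", and it allows for events that patients volunteer between visits. Section 9.2.1 asks for 30 days of follow-up from the last dose when a subject discontinues study drug. It names no visit or call for this.

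**The concern.** Sections 10.1 and 10.3 define a period in which events count, and 6.5.1 sets the occasions on which staff ask about them. For a subject who takes the full course, the last marked occasion comes before the period ends.

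Safety and tolerability is the secondary objective (2.2.2). Therapy-related SAEs and grade 3 or higher events are secondary endpoints (4.1.1.2) with no stated time point, so their counts rest on this collection. Tendon rupture and cardiac arrhythmia are named SAE outcomes in 10.3, and nerve symptoms are a named risk in 10.4.1.1. None of these has another scheduled route of capture after month 3. If sites follow the table, events late in the window are recorded only when a patient happens to raise them or they come to light in routine care. The endpoint counts would then be too low by an unknown amount.

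**Working it through.** The plan gives no figure on this point to reproduce. The check is calendar arithmetic.

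**Inputs**
- Post-dose window: 28 days (10.1, 10.3).
- Last dose: day 90 (6.4.2), or day 96 to 97 if 90 days of dosing begin on day 7 (4.1, 6.4.1). With the first dose on day 7, the 90th falls on 7 + 89 = 96; adding 90 full days gives 7 + 90 = 97.
- Month-3 visit: ±14 days, the fifth entry in the visit-window row of 6.5.1. The row as read has six entries for eight columns and may be misaligned, so ±7 days was also tried.
- Assumption: month 3 is day 90, varied from 89 to 92, and month 6 is day 180 or 183. The documents give no conversion to days.

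**Formulas**
- Window closes = last dose + 28.
- Time with no scheduled assessment = window closes − day of month-3 visit.

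**Results with month 3 at day 90 (visit on day 76, 90 or 104)**

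| Last dose | Window closes | Earliest visit | Nominal visit | Latest visit |
|---|---|---|---|---|
| Day 90 | Day 118 | 118 − 76 = 42 | 118 − 90 = 28 | 118 − 104 = 14 |
| Day 96 | Day 124 | 124 − 76 = 48 | 124 − 90 = 34 | 124 − 104 = 20 |
| Day 97 | Day 125 | 125 − 76 = 49 | 125 − 90 = 35 | 125 − 104 = 21 |

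**Extremes with month 3 varied from day 89 to day 92**
- Shortest: month 3 at day 92, visit 14 days late (day 106), last dose day 90: 118 − 106 = 12 days.
- Longest: month 3 at day 89, visit 14 days early (day 75), last dose day 97: 125 − 75 = 50 days.
- With ±7 days, the latest permitted visit still leaves 19 days (118 − 99) to 29 days (125 − 96).

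No combination reaches zero. A visit on day 76 also leaves 90 − 76 = 14 days of dosing after the last scheduled assessment.

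**If 10.1 governs and AEs are asked about at month 6**
- Earliest: (180 − 14) − 125 = 41 days after the window closes.
- Latest: (183 + 14) − 118 = 79 days after it closes.
- This is roughly 6 to 11 weeks.

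**9.2.1 against 10.1 and 10.3.** The periods are 30 and 28 days, a difference of 2 days. For a last dose on day 90 they end on day 120 and day 118.

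**The case against.** The strongest reply is that 10.1 already requires what is missing. Questioning at every visit includes month 6, and 10.1 adds volunteered reports and findings from examinations and laboratory tests. Section 9.2.1 asks for 30 days of follow-up, which outlasts the 28-day window. Several outcomes have their own routes: infections are endpoints at 6 months (4.1.1.2), cultures where applicable and creatinine are listed at month 6 (6.5.1), and graft loss and death are tracked to 1 year (4.1.1.3).

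Much of this stands. A reader might infer from the table that late events in full-course subjects are never asked about. The documents do not support that, because they do not say whether the table or 10.1 governs.

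The reply does not remove the gap in the schedule, for four reasons:
- Section 6.5.3 defines study completion by the evaluations in 6.5.1. A subject can therefore complete with no AE assessment after month 3.
- Concomitant medication is the only research-funded row still marked at months 6, 9 and 12, and footnote 2 reduces it to immunosuppressant dosages. The blank AE cells fit that pattern and do not look like a slip.
- The heading of 9.2.1 suggests early stopping. Even if it is read as covering any end of dosing, it has no contact in the schedule.
- Volunteered reporting is not systematic ascertainment.

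A reader might also infer that ascertainment differs by arm. A subject who stops drug by day 62 has a window that closes by a nominal month-3 visit (62 + 28 = 90), so coverage does depend on time on drug. But the documents give no discontinuation rates by arm. Nor does 6.5.3 say when the final safety visit after withdrawal takes place, so it cannot be assumed to cover the 4 weeks after the last dose.

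**Conclusion.** The point holds as a contradiction between the schedule and the text, with a gap in scheduled assessment. For a full-course subject, the time between the last scheduled AE/SAE assessment and the close of the window is 28 days nominally. It is 14 to 42 days across the visit window as read, and 12 to 50 days over all readings tried.

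The size depends on which end of dosing is meant, how months convert to days, and whether the ±14-day entry belongs to month 3. The existence of the gap depends on none of these. It is not expressed as a share of the safety window, because the documents give only a latest day for the first dose.

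The consequence is possible under-recording of AEs and SAEs that have no other scheduled route. The number of events missed cannot be estimated from the documents. The primary endpoint rests on plasma PCR and biopsy and is not affected.

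**What to change.** Mark AE/SAE Assessment in the month-6 column of 6.5.1. Add a footnote telling staff to record every AE and SAE with onset between the previous visit and the end of the post-dose window. Then reconcile 6.5.1, 9.2.1, 10.1 and 10.3 on two matters: which visits include AE questioning, and whether follow-up after the last dose is 4 weeks or 30 days. Section 9.2.1 should also say whether it applies to subjects who finish the course, and which contact carries it out.

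The cost is one mark, one footnote and a few minutes of questioning at a visit that already exists. No new visit or test is needed. The downside is longer recall, since month 6 falls weeks after the window closes. Also, footnote 2 does not require antimicrobial use to be recorded at that visit, so the AE form would have to hold that detail for late infections.

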### **10.3 Serious Adverse Event**

A Serious Adverse Event (SAE) is any adverse event occurring for up to 4 weeks after completion of study drug administration that results in any of the following outcomes:

- Death
- Graft loss
- A life threatening event which may place the patient at an immediate risk of death
- Persistent or significant disability
- Hospitalization for administration of intravenous antibiotics due to presence of multidrug resistant infection
- Cardiac arrhythmia
- Tendon rupture

SAEs considered "definitely" related to the study drug must be submitted to IRB.

### **10.4 Potential Risks and Discomforts**

#### **10.4.1 Risks**

##### **10.4.1.1 Ciprofloxacin**

The most common adverse effects associated with ciprofloxacin in clinical trials were nausea (2.5%), diarrhea (1.6%), liver function test abnormalities (1.3%) vomiting (1%) and rash (1%).

Fluoroquinolone antibiotics, including ciprofloxacin, have been associated with an increased risk of tendinitis and tendon rupture. The risk may be increased in patients over the age of 60, and in kidney, heart, and lung transplant recipients. Patients should be advised to report signs of tendonitis or tendon pain, swelling, or inflammation immediately. Overall, musculoskeletal adverse effects occur in less than 1% of adults treated with ciprofloxacin.

Fluoroquinolone antibiotics, including ciprofloxacin, have the potential to cause QT prolongation and should be used cautiously in patients with known QT prolongation, and in those taking concomitant medications that are known to prolong the QT interval.

Fluoroquinolone antibiotics, including ciprofloxacin, should be used cautiously in patients with central nervous system disorders. Seizures have occurred in <1% although the risk can be increased in cases of overdosage.

All antibacterial agents alter the normal flora of the gastrointestinal tract and promote the growth of clostridia.

Other potential risks associated with fluoroquinolone antibiotics include sensitivity to the sun, sunburn like reactions, nerve pain, including tingling, burning, numbness, or weakness, tremors, hallucinations, depression and convulsions.

#### **10.4.1.2 Risks associated with Blood Draws**

The risk associated with multiple blood draws for PK assessments will be the increased potential for hematoma at the blood draw site.

#### **10.4.2 Potential Benefits**

This study will improve the knowledge of a potential prophylaxis strategy against BK virus in transplant recipients. Current data demonstrated increased graft loss among patients developing BK virus and BK nephropathy. Knowledge about possible preventative strategies may lead to reductions in BK-related adverse outcomes.

### **11 Ethics**

#### **11.1 Responsibilities of the Investigator**

The Principal Investigator will maintain complete study files (electronic and/or paper) to enable full documentation of the study procedures and data for purpose of verification and study analysis.

The Principal Investigator, or his designee, will explain the nature of the study to the subject, inform the subject that participation is voluntary, and that withdrawal at any time is allowed. The Principal Investigator will maintain documentation of written informed consent.

This study will be conducted using Good Clinical Practice as identified by

- International Conference on Harmonization (ICH) Tripartite Guidelines for Good Clinical Practice
- US Code of Federal Regulation (CFR) dealing with clinical studies (21 CFR parts 50, 54, 56 and 312)
- The principles stated in the Declaration of Helsinki concerning medical research in humans

#### **11.2 Institutional Review Board Approval**

This study will be reviewed and approved by The Methodist Hospital Research Institute Institutional Review Board (TMHRI IRB) prior to commencement of any subject-specific activities. A current letter of IRB approval will be maintained with the study files. No changes to the protocol or informed consent form will be made prior, to or without documented approval from TMHRI IRB.

All subjects will provide consent (indicated by their signature or their legally authorized representative's signature on the approved Informed Consent Form) prior to initiation of any study-related activities. Signed and dated ICFs will be maintained with the study archives.

## **12 Data Handling and Recordkeeping**

### **12.1 Confidentiality**

In order to maintain confidentiality, the subject will be identified only by his/her study screening number and/or randomization number.

### **12.2 Flow of Information and Records to be Kept**

Throughout the conduct of this study, all required data will be recorded in electronic CRFs that have been specifically designed to record all observations and other data pertinent to this clinical investigation. Data reported on eCRFs should be consistent with source documents when applicable, or the discrepancies should be explained. Any change or correction to a CRF will produce an audit trail within the eCRF system and will identify the user, date and time of the change.

The eCRFs should be completed in a timely fashion. The complete eCRFs will be maintained by the study site, as is required by institutional, local and government regulations.

The clinical investigator is responsible for maintaining adequate and accurate records as specified in Essential Documents for the Conduct of a Clinical Trail (section 8 of the ICH Guideline for Good Clinical Practice) to enable the conduct of the study to be fully documented, and the study data to be subsequently verified. The clinical investigator must notify the Sponsor prior to destroying any clinical study records.

Upon study termination, original documents will be maintained at TMHRI.

## **13 Financing**

Funding for this study will be provided by the Methodist Hospital Department of Surgery and the Methodist Hospital Department of Pharmacy.

## **14 Publication Policy**

The Principal Investigator holds final approving authority over whether or not any proposed publication (eg, abstract, manuscript) based on the data generated from this study can or should be submitted for publication to journals, scientific meetings, or any other medium.

## 16 Appendices

### 16.1 Appendix 1: Ciprofloxacin Package Insert

The package insert for ciprofloxacin can be found at the following URL:

<http://www.univgraph.com/bayer/inserts/ciprotab.pdf>

### 16.2 Appendix 2: Equation for Estimating Glomerular Filtration Rate

IDMS-traceable MDRD equation for estimating Glomerular Filtration Rate (eGFR).

$GFR \text{ (mL/min/1.73 m}^2\text{)} = 175 \times (S_{cr})^{-1.154} \times (\text{Age})^{-0.203} \times (0.742 \text{ if female}) \times (1.212 \text{ if African American})$  (conventional units)
